4.3.1 Re-initiation Dose Schedules

Subjects in the cohorts listed in Table 4.3.1-1 who met eligibility criteria for re-initiation of treatment (Section 3.1.4.8) will receive treatment as presented below:

Table 4.3.1-1: Treatment Schedules for Re-Initiation

Cohort	Treatment upon Re-initiation
mStage 1/2	Nivolumab 480 mg Q4W
cStage 1/2	Nivo 240 mg + Ipi 1 mg/kg Q3W for 4 doses, followed by Nivolumab 480 mg (Q4W)
C3 (1L)	Nivo 360mg Q3W + Ipi 1mg/kg Q6W
C5 (BMS-986016 /anti-LAG3)	Nivo 240mg Q2W + BMS-986016 (LAG3) 160mg Q2W

Note: "Re-initiation" relates to maximum clinical benefit participants.

Protocol Amendment No: 09

Treatment duration after re-initiation, inclusive of treatment beyond progression will be a maximum of 24 months.

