Table 5.1-2: Short-Term Procedural Outline (Nivolumab Monotherapy, CA209142): MSI-H (Arm N, mStage 1/2)			
Procedure	During Treatment Day 1 every 4 weeks See Section 3.1.4.1 for treatment duration	Notes Visit Window : ± 2 Days	
MSI Status Determination			
Submit Redacted Pathology Report to BMS Containing Local MSI Results	To be submitted at Week 1 Day 1. Report must contain MSI results and should also contain specific results per markers tested for MSI.		
Clinical Drug Supplies			
IVRS Drug Vial Assignment	X	Vials may be assigned up to 2 days prior to first dose date.	
Dispense Study Drug	X	Within 3 days from vial allocation, the subject must receive the first dose of study medication. Subjects may be dosed no less than 25 days between doses. The dosing calculations should be based on the body weight. All doses should be rounded to the nearest milligram.	

Protocol Amendment No: 09 Date: 27-Aug-2021

Approved v1000 930073805 10.0

Table 5.1-3: Short-term Procedural Outline (Nivolumab Ipilimumab Combination, CA209142): MSI-H (Arm N +I, cStage 1/2) and non-MSI-H (Independent Safety Study)

Procedure	During Treatment Day 1 (Dose 1/week 1, Dose 2/week 4, Dose 3/week 7, Dose 4/week 10)	During Treatment Day 1 (week 13 and every 4 weeks thereafter)	Notes Visit Window : ± 2 Days
	For MSH-H (Arm N+l 3.1.4.1 for treatm		
Safety Assessments			
Targeted Physical Examination	X	X	Targeted examination must include at a minimum the following body systems: Cardiovascular Gastrointestinal Pulmonary Neurological exam for subjects with brain metastases
Vital Signs	X	X	Including BP, HR, and temperature. Obtain vital signs within 72 hours prior to first dose
Physical Measurements (including performance status)	X	X	Weight and ECOG performance status. See Appendix 2 for ECOG Performance Status scale.
Review of Concomitant Medication	X	X	
Adverse Events Assessment	X	X	
Laboratory Tests	X	X	On-study local laboratory assessments (after first dose) should be done within 72 hours prior to each dose and include: CBC w/differential and platelet count, LFTs (ALT, AST, total bilirubin, alkaline phosphatase), BUN or serum urea level, creatinine, Ca, Mg, Na, K, Cl, LDH, glucose, amylase, lipase, TSH with reflexive Free T4, Free T3.

Date: 27-Aug-2021

Approved v1000 930073805 10.0

Table 5.1-3: Short-term Procedural Outline (Nivolumab Ipilimumab Combination, CA209142): MSI-H (Arm N +I, cStage 1/2) and non-MSI-H (Independent Safety Study)

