Laboratory Tests	X	CBC w/differential and platelet count, Chemistry panel including: LDH, AST, ALT, ALP, T.Bili, BUN or serum urea level, creatinine, Ca, Mg, Na, K, Cl, Glucose, amylase, lipase, TSH, Free T4, Free T3, Hepatitis B surface antigen (HBV sAg), and hepatitis C antibody (HCV Ab) or Hepatitis C RNA (HCV RNA), within 14 days prior to first dose. Safety laboratory tests do not need to be repeated if they were performed within 14 days of first dose. Performed for the C5 Cohort Only: Cardiac Troponin Levels: T (cTnt) or I (cTnI)	
Pregnancy Test (WOCBP only)	X	Serum or urine to be done at screening visit and repeated within 24 of first dose of study therapy	
Efficacy Assessment			
Re-initiation Baseline Tumor Imaging Assessment	X	CT or MRI chest, abdomen, pelvis and all known or suspected sites of disease within 28 days prior to first dose of re-initiation treatment.	

Protocol Amendment No: 09 Date: 27-Aug-2021

Approved v1000 930073805 10.0

151

Table 5.1-9: Re-initiation Procedural Outline (Nivolumab Monotherapy, CA209142): MSI-H (Arm N, mStage 1/2)

Procedure	Nivolumab 480 mg Q4W See Section 4.3.1 for Re-initiation Treatment Schedule and Duration To Be Performed at Each Dosing Visit	Notes Visit Window : ± 2 Days
Safety Assessments		
Targeted Physical Examination	X	Targeted examination must include at a minimum the following body systems: Cardiovascular Gastrointestinal Pulmonary Neurological exam for subjects with brain metastases
Vital Signs	X	Including BP, HR, and temperature. Obtain vital signs within 72 hours prior to first dose.
Physical Measurements (including performance status)	X	Weight and ECOG performance status. See Appendix 2 for ECOG Performance Status scale.
Review of Concomitant Medication	X	
Adverse Events Assessment	X	
Laboratory Tests	X	On-study local CBC, chemistry, and thyroid laboratory assessments (after first dose) should be done within 72 hours prior to each dose every 4 weeks and include: CBC w/differential and platelet count, LFTs (ALT, AST, total bilirubin, alkaline phosphatase), BUN or serum urea level, creatinine, Ca, Mg, Na, K, Cl, LDH, glucose, amylase, lipase, TSH with reflexive Free T4, Free T3.
Pregnancy Test (WOCBP only)	X	Serum or urine pregnancy test to be done within 24 hours prior to first dose, and then every 4 weeks (± 1 week) regardless of dosing schedule

Protocol Amendment No: 09

Table 5.1-9: Re-initiation Procedural Outline (Nivolumab Monotherapy, CA209142): MSI-H (Arm N, mStage 1/2)

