Procedure	Nivolumab 480 mg Q4W See Section 4.3.1 for Re-initiation Treatment Schedule and Duration To Be Performed at Each Dosing Visit	Notes Visit Window : ± 2 Days
Efficacy Assessments		
Tumor Imaging Assessment		See separate Table 5.1-14
Exploratory Biomarker Testing		
Soluble Biomarkers (Serum)		See separate Table 5.6.8-4
Peripheral Blood Mononuclear Cells (PBMCs) Immuno-phenotyping	See separate Table 5.6.8-4	
Ex vivo Functional assay (PBMCs)		See separate Table 5.6.8-4
Tumor tissue sample (biopsy) (optional)	See separate Table 5.6.8-4	
Whole blood gene expression	See separate Table 5.6.8-4	
Plasma Sample	See separate Table 5.6.8-4	
SNP (whole blood)	See separate Table 5.6.8-4	
Clinical Drug Supplies		
IVRS Drug Vial Assignment	X	Vials may be assigned up to 2 days prior to first dose date.
Dispense Study Drug	X	Within 3 days from vial allocation, the subject must receive the first dose of study medication. Following first nivolumab dose, subsequent nivolumab dosing will be based on the actual date of administration of the previous dosing. Subjects may be dosed within a ± 3-day window of scheduled dose due to scheduling conflict. Subjects may be dosed no less than 25 days from the previous dose.

Table 5.1-10: Re-initiation Procedural Outline (Nivolumab Ipilimumab Combination, CA209142): MSI-H (Arm N+I, cStage 1/2)

Procedure	See Section 4.3.1 for Re-initiation Treatment Schedule and Duration To Be Performed at Each Dosing Visit	Notes Visit Window : ± 2 Days
Safety Assessments		
Targeted Physical Examination	X	Targeted examination must include at a minimum the following body systems: Cardiovascular Gastrointestinal Pulmonary Neurological exam for subjects with brain metastases
Vital Signs	X	Including BP, HR, and temperature. Obtain vital signs within 72 hours prior to first dose
Physical Measurements (including performance status)	X	Weight and ECOG performance status. See Appendix 2 for ECOG Performance Status scale.
Review of Concomitant Medication	X	
Adverse Events Assessment	X	
Laboratory Tests	X	On-study local laboratory assessments (after first dose) should be done within 72 hours prior to each dose every 4 weeks and include: CBC w/differential and platelet count, LFTs (ALT, AST, total bilirubin, alkaline phosphatase), BUN or serum urea level, creatinine, Ca, Mg, Na, K, Cl, LDH, glucose, amylase, lipase, TSH with reflexive Free T4, Free T3.

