Pregnancy Test (WOCBP only)	X	Serum or urine pregnancy test to be done within 24 hours prior to first dose, and then every 4 weeks (± 1 week) regardless of dosing schedule
Efficacy Assessments		
Tumor Imaging Assessment		See separate Table 5.1-14

Table 5.1-10: Re-initiation Procedural Outline (Nivolumab Ipilimumab Combination, CA209142): MSI-H (Arm N+I, cStage 1/2)

Procedure	See Section 4.3.1 for Re-initiation Treatment Schedule and Duration To Be Performed at Each Dosing Visit	Notes Visit Window : ± 2 Days
Exploratory Biomarker Testing		
Soluble Biomarkers (Serum)		See separate Table 5.6.8-5
Peripheral Blood Mononuclear Cells (PBMCs) Immuno- phenotyping		See separate Table 5.6.8-5
Ex vivo Functional assay (PBMCs)		See separate Table 5.6.8-5
Tumor tissue sample (biopsy) (optional)		See separate Table 5.6.8-5
Whole blood gene expression		See separate Table 5.6.8-5
Plasma Sample		See separate Table 5.6.8-5
SNP (whole blood)	See separate Table 5.6.8-5	
Clinical Drug Supplies		
IVRS Drug Vial Assignment	X	Vials may be assigned up to 2 days prior to first dose date.
Dispense Study Drug	X	Within 3 days from vial allocation, the subject must receive the first dose of study medication. Following first nivolumab dose, subsequent nivolumab dosing will be based on the actual date of administration of the previous dosing. Subjects may be dosed within a ± 3-day window of scheduled dose due to scheduling conflict. Subjects may be dosed no less than 19 days between doses for the first 4 doses of nivolumab and ipilimumab. For the remaining doses, subjects may be dosed no less than 25 days between doses of nivolumab.

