Table 5.1-11: Re-initiation Schedule for C3 Cohort [Nivolumab 360 mg Q3W + Ipilimumab 1 mg/kg Q6W] No Prior **Treatments in Metastatic Setting** Notes To Be Performed at Each Dosing Visit, **Visit Window: ± 2 Days Unless Otherwise Specified in Notes or Procedure** See Section 4.3.1 for Re-initiation Treatment Schedule and Separate Table Duration **Safety Assessments** Targeted examination must include at a minimum the following body systems: Cardiovascular X **Targeted Physical Examination** Gastrointestinal Pulmonary Neurological exam for subjects with brain metastases Including BP, HR, temperature. Obtain vital signs within 72 hours prior Vital Signs X to first dose. Weight and ECOG performance status. Physical Measurements (including X performance status) See Appendix 2 for ECOG Performance Status scale. Review of Concomitant X Medication Adverse Events Assessment Χ On-study local laboratory assessments (after first dose) should be done within 72 hours prior to each dose through Week 23 and every dose thereafter and include: Χ CBC w/differential and platelet count, **Laboratory Tests** LFTs (ALT, AST, total bilirubin, alkaline phosphatase), BUN or serum urea level, creatinine, Ca, Mg, Na, K, Cl, LDH, glucose, amylase, lipase, TSH with reflexive Free T4, Free T3. Serum or urine pregnancy test to be done within 24 hours prior to first Pregnancy Test (WOCBP only) X dose, and then every 4 weeks (± 1 week) regardless of dosing schedule

Table 5.1-11: Re-initiation Schedule for C3 Cohort [Nivolumab 360 mg Q3W + Ipilimumab 1 mg/kg Q6W] No Prio Treatments in Metastatic Setting			
Procedure	To Be Performed at Each Dosing Visit, Unless Otherwise Specified in Notes or Separate Table	Notes Visit Window: ± 2 Days See Section 4.3.1 for Re-initiation Treatment Schedule and Duration	
Efficacy Assessments			
Tumor Imaging Assessment		See separate Table 5.1-14	
Exploratory Biomarker Testing			
Soluble Biomarkers (Serum)		See separate Table 5.6.8-5	
Peripheral Blood Mononuclear Cells (PBMCs) Immuno- phenotyping	See separate Table 5.6.8-5		
Ex vivo Functional assay (PBMCs)	See separate Table 5.6.8-5		
Tumor tissue sample (biopsy) (optional)	See separate Table 5.6.8-5		
Whole blood gene expression	See separate Table 5.6.8-5		
Plasma Sample	See separate Table 5.6.8-5		
SNP (whole blood)	See separate Table 5.6.8-5		
Clinical Drug Supplies			
IVRS Drug Vial Assignment	X	Vials may be assigned up to 2 days prior to first dose date.	

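### The laboratory note for cStage 1/2 re-initiation (Table 5.1-10) contradicts its own column header and the 3-weekly combination phase, so the timing of safety laboratories before doses 2 to 4 is ambiguous

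*Combined protocol and SAP*

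**What the plan says.** Five places in the protocol bear on this.

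- **Regimen.** For cStage 1/2, Table 4.3.1-1 (Section 4.3.1) gives "Nivo 240 mg + Ipi 1 mg/kg Q3W for 4 doses, followed by Nivolumab 480 mg (Q4W".
- **Dosing interval.** The study-drug row of Table 5.1-10 recognises the 3-weekly phase: "Subjects may be dosed no less than 19 days between doses for the first 4 doses of nivolumab and ipilimumab".
- **Column header.** The laboratory row of Table 5.1-10 has an X under "See Section 4.3.1 for Re-initiation Treatment Schedule and Duration To Be Performed at Each Dosing Visit". The header makes no exception for notes.
- **Laboratory note.** The note beside that X reads "On-study local laboratory assessments (after first dose) should be done within 72 hours prior to each dose every 4 weeks and include".
- **First dose.** The note applies after the first dose. Laboratories for the first re-initiation dose come from re-initiation screening (Table 5.1-8), which says "Safety laboratory tests do not need to be repeated if they were performed within 14 days of first dose".

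Three neighbouring tables serve as comparators. Table 5.1-9 (mStage re-initiation, nivolumab every 4 weeks) has the same words, "within 72 hours prior to each dose every 4 weeks and include". Table 5.1-3 (initial treatment of the same combination arm, 3-weekly for four doses and then 4-weekly) reads "On-study local laboratory assessments (after first dose) should be done within 72 hours prior to each dose and include". Table 5.1-11 (C3 re-initiation, nivolumab 3-weekly) asks for laboratories at every dose, under a header that lets notes override it: "To Be Performed at Each Dosing Visit, Unless Otherwise Specified in Notes or Separate Table".

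**The concern.** The note joins two instructions, one tied to each dose and one tied to a 4-week interval. They coincide only when dosing is 4-weekly. In the first four re-initiation doses of cStage 1/2 it is not, so a site cannot follow the note as written and has to choose which half to obey.

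The choice matters because these four doses are the only ipilimumab doses in the re-initiation regimen. They are given to subjects who progressed up to 52 weeks after their last dose (Section 3.1.4.8). The panel in this row includes the liver tests, creatinine, amylase, lipase and platelets that feed the delay and discontinuation criteria in Sections 4.3.3 and 4.3.6. There is also a smaller analytical consequence. Section 8.4.7.2 repeats selected safety analyses in re-initiated subjects. If those include the worst-grade laboratory summaries of Section 8.4.3, sites that read the note differently would detect abnormalities with different frequency.

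**Working it through.** No sample size, power or error rate is involved, and the plan gives no figure to reproduce. The check lays the dosing schedule over the laboratory schedule under each reading.

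**Inputs**
- Combination doses: four, 21 days apart (Table 4.3.1-1).
- Laboratory window: the 72 hours before a dose, that is, Day d − 3 to Day d (Table 5.1-10).
- Literal 4-weekly grid: every 28 days from re-initiation Day 1.
- Tolerances in Table 5.1-10: visit window ±2 days, dosing window ±3 days, minimum 19 days between the first four doses.

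**Reading A: the header governs.** Every dosing visit has a panel. Dose 1 is covered by screening, and doses 2, 3 and 4 by the row itself. Combination doses without a panel: 0 of 4.

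**Reading B: a literal 4-weekly interval.**
- Dose k falls on Day 1 + 21(k − 1): Days 1, 22, 43, 64 (Weeks 1, 4, 7, 10).
- Panel j falls on Day 1 + 28(j − 1): Days 1, 29, 57, 85 (Weeks 1, 5, 9, 13).

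| Dose | Day | 72-hour window | Panel in window? | Last panel | Age at dosing |
|---|---|---|---|---|---|
| 2 | 22 | 19–22 | none | Day 1 | 22 − 1 = 21 days (3 weeks) |
| 3 | 43 | 40–43 | none | Day 29 | 43 − 29 = 14 days (2 weeks) |
| 4 | 64 | 61–64 | none | Day 57 | 64 − 57 = 7 days (1 week) |

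Three doses are uncovered. The 21 days for dose 2 assumes a panel on Day 1. A screening panel that is not repeated may be up to 14 days earlier.

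**Sensitivity of Reading B**
- Moving each panel by ±2 days leaves all three doses uncovered. The nearest approach is Day 57 + 2 = 59, still before Day 61.
- Let each of the three intervals also vary from 19 days (the minimum) to 21 + 3 = 24 days, which gives 6 × 6 × 6 = 216 combinations. Three doses are uncovered in 181 and two in 35. In those 35, dose 4 falls by Day 62, so a panel on Day 59 just enters its window. Doses 2 and 3 are never covered.

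**After dose 4.** The protocol does not state the interval from dose 4 to the first 4-weekly nivolumab dose on re-initiation. If that dose falls at Week 13 (Day 85), as in initial treatment, the grid realigns. If it falls 28 days after dose 4 (Day 64 + 28 = 92), a fixed grid from Day 1 does not, since the preceding panel is at Day 85, 7 days earlier. Realignment at Week 13 is therefore an assumption. The count for doses 2 to 4 does not depend on it.

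**The case against.** The strongest reply is that the header settles the matter. It places the panel at every dosing visit, has no exception for notes (unlike Table 5.1-11), and agrees with the half of the note that refers to each dose. A panel at Week 5 or Week 9 would also break the note's own 72-hour condition, because no dose follows within that time. The 4-week phrase may simply be left from a 4-weekly regimen. The wording shared with Table 5.1-9 fits that explanation, but it remains an inference.

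Most of this stands, and Reading A is the more natural one. It does not close the question, because in this table the header does not reliably override notes. The next row, pregnancy testing, carries an X under the same header, while its note sets a 4-weekly interval independent of dosing. That note says openly that it is detached from the dosing schedule and the laboratory note does not, which favours Reading A. Even so, it shows a site that a note here can set its own interval.

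A reader might draw three stronger conclusions, none of which the documents support:

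- **That three combination doses have no scheduled laboratories.** This follows only on Reading B. On Reading A the number is zero.
- **That the delay and discontinuation criteria could not be applied.** Sections 4.3.3 and 4.3.6 are triggered by abnormalities and set no 72-hour precondition. Adverse events are assessed at every dosing visit, and Section 5.3 provides for further tests when clinically indicated. Elsewhere the protocol openly accepts doses without a scheduled panel: in the initial C3 and C5 schedules (Tables 5.1-4 and 5.1-5), laboratories move to alternate doses after Week 23.
- **That the combination toxicity rates in Section 1.4.2.1 measure the harm.** They pool 53 melanoma subjects, mostly from cohorts given ipilimumab 3 mg/kg and some with higher cumulative doses than planned here. Re-initiation uses 1 mg/kg in subjects required to have tolerated study drug (Section 4.3.9).

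**Conclusion.** The point holds as an internal inconsistency in an operative safety schedule. The Table 5.1-10 laboratory note is wrong as written for the 3-weekly phase: it conflicts with its own header, with Table 4.3.1-1 and with the 19-day minimum interval stated in the same table. The conflict itself needs no assumption.

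Its size depends on how a site resolves it: no combination dose affected if the header governs, and three of four at nominal timing if the 4-week interval is taken literally. The second figure assumes a fixed 28-day grid from re-initiation Day 1. It falls to two in a minority of permitted dose timings. The documents do not show that any site reads the note that way, so a monitoring gap is possible but not established.

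**What to change.** The sponsor should reconcile the laboratory note in Table 5.1-10 with its column header and with Table 4.3.1-1. The row should state one unambiguous laboratory timing for the 3-weekly combination phase and one for the 4-weekly nivolumab phase. It should also say whether each is counted from the dose or from the calendar, since the interval after dose 4 is not given. Which timing applies is for the sponsor to decide.

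The edit is one table cell. If the reconciled text follows the header, nothing is added to what the header already asks. Compared with a literal 4-weekly reading, that would add at most three local panels per re-initiated cStage subject (doses 2, 3 and 4), at visits already scheduled.

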5.2 Study Materials

- NCI CTCAE version 4.0
- Nivolumab Investigator Brochure
- Ipilimumab Investigator Brochure
- BMS-986016 Investigator Brochure
- Daratumumab Investigator Brochure
- Pharmacy Binder
- Laboratory manuals for collection and handling of blood (including biomarker and immunogenicity) and tissue specimens
- Site manual for operation of interactive voice response system, including enrollment worksheets
- Manual for entry of local laboratory data
- Pregnancy Surveillance Forms
- RECIST 1.1 pocket guide

5.3 Safety Assessments

At baseline, a medical history will be obtained to capture relevant underlying conditions. The baseline examinations should include signs and symptoms, weight, height, ECOG Performance Status, BP, HR, and temperature, and they should be performed within 14 days prior to first dose except where noted in Table 5.1-1. Concomitant medications will also be collected within 14 days prior to first dose and through the study treatment period (See Table 5.1-1, Table 5.1-2 Table 5.1-3, Table 5.1-4, Table 5.1-5, and Table 5.1-6) and during the re-initiation period if applicable Table 5.1-8, Table 5.1-9, Table 5.1-10, Table 5.1-11 and Table 5.1-12.

Baseline local laboratory assessments should be done within 14 days prior to the first dose and include: CBC w/differential, LFTs (ALT, AST, total bilirubin, alkaline phosphatase), BUN or serum urea level, creatinine, Ca, Mg, Na, K, Cl, LDH, glucose, amylase, lipase, TSH, Free T4, Free T3, and Hep B and C testing (HBV sAg and HCV RNA or Ab) (see Table 5.1-1). Pregnancy testing for WOCBP (done locally) should be done within 24 hours prior to first dose, and then every 4 weeks (±1 week) regardless of dosing schedule and during re-initiation period, as applicable, and at each safety follow-up visits after the original treatment phase and after re-initiated treatment.

Subjects will be evaluated for safety if they have received any study drug. Toxicity assessments will be performed continuously during the treatment phase and during re-initiated treatment if applicable. During the safety follow-up phase (Table 5.1-7 and Table 5.1-13), toxicity assessments should be done in person. Once subjects reach the survival follow-up phase, either in-person visits or documented telephone calls to assess the subject's status are acceptable.

Adverse events and laboratory values will be graded according to the NCI-CTCAE version 4.0.

Protocol Amendment No: 09

Clinical Protocol CA209142 BMS-936558 nivolumab

On-study weight, ECOG Performance Status, and vital signs should be assessed at each on-study visit prior to nivolumab dosing. Vital signs should also be taken as per institutional standard of care prior to, during and after dosing. The start and stop time of the nivolumab, ipilimumab, BMS-986016, and daratumumab infusions should be documented. Physical examinations are to be performed as clinically indicated. If there are any new or worsening clinically significant changes since the last exam, report changes on the appropriate non-serious or serious adverse event page.

Additional measures, including non-study required laboratory tests, should be performed as clinically indicated or to comply with local regulations. Laboratory toxicities (eg, suspected drug inducted liver enzyme elevations) will be monitored during the follow-up phase via on site/local labs until all study drug related toxicities resolve, return to baseline or are deemed irreversible.

Some of the previously referred to assessments may not be captured as data in the eCRF. They are intended to be used as safety monitoring by the treating physician. Additional testing or assessments may be performed as clinically necessary or where required by institutional or local regulations.

